11.13.8. Pharmacokinetic Tables

Pharmacokinetic Tables					
No.	Population	IDSL / TST ID / Example Shell	Title	Programming Notes	Deliverable [Priority]
PK Concentration Data					
4.01	PK	PK01	Summary of Plasma GSK2798745 Pharmacokinetic Concentration-Time Data (ng/mL)		SAC [2]
4.02	Per Protocol	PK01	Summary of Plasma GSK2798745 Pharmacokinetic Concentration-Time Data (ng/mL)	Add Footnote	SAC [2]
PK Derived Parameters					
4.03	PK Parameter	PKPT1	Summary Statistics of Derived Plasma GSK2798745 Pharmacokinetic Parameters	Parameters with units	SAC [2]
4.05	PK Parameter	PKPT3	Summary Statistics of Log-Transformed Derived Plasma GSK2798745 Pharmacokinetic Parameters	Parameters with units	SAC [2]

11.13.9. Pharmacokinetic Figures

Pharmacokinetic Figures					
No.	Population	IDSL / TST ID / Example Shell	Title	Programming Notes	Deliverable [Priority]
Individual Plots					
4.01	PK	PKCF1P	Individual GSK2798745 Plasma Concentration-Time Plot by Treatment (Linear and Semi-Log)	Paginate by Treatment	SAC [2]
Mean / Median Plots					
4.02	PK	PKCF2	Mean Plasma GSK2798745 Concentration-Time Plots by Treatment (Linear and Semi-log)	Paginate by Treatment	SAC [2]

11.13.10. ICH Listings

ICH Listings					
No.	Population	IDSL / TST ID / Example Shell	Title	Programming Notes	Deliverable [Priority]
Randomisation					
01	All Subjects	TA2	Listing of Randomised and Actual Treatments		SAC [2]
Subject Disposition					
02	All Subjects	ES3	Listing of Reasons for Study Withdrawal		SAC [2]
03	All Subjects	ES7	Listing of Reasons for Screening Failure		SAC [2]
04	All Subjects	SA3b	Listing of Subjects Excluded from Per Protocol Population	Only list subject that deviate from per protocol	SAC [2]
05	All Subjects	DV2	Listing of Important Protocol Deviations		SAC [2]
06	All Subjects	IE4	Listing of Subjects with Inclusion/Exclusion Criteria Deviations		SAC [2]
Demographics					
07	All Subjects	DM4	Listing of Demographic Characteristics		SAC [2]
08	All Subjects	DM10	Listing of Race		SAC [2]
Medical Conditions & Concomitant Medication					
09	All Subjects	MH3	Listing of Medical Conditions (Current/Past)		SAC [2]
10	All Subjects	CM5	Listing of Concomitant Medication		SAC [2]

ICH Listings					
No.	Population	IDSL / TST ID / Example Shell	Title	Programming Notes	Deliverable [Priority]
Exposure					
11	All Subjects	EX4	Listing of Exposure		SAC [2]
Adverse Events					
12	All Subjects	AE9	Listing of All Adverse Events		SAC [2]
13	All Subjects	AE9	Listing of Serious Adverse Events	Only include AE's classified as serious	SAC [2]
14	All Subjects	AE9	Listing of Adverse Events Leading to Withdrawal from Study / Permanent Discontinuation of Study Treatment.		SAC [2]
15	All Subjects	ECSSRS4	Listing of C-SSRS		SAC [2]
16	All Subjects	EFF_L1	Listing of SNAQ		SAC [2]
17	All Subjects	EFF_L1	Listing of Audiometry		SAC [2]
18	All Subjects	EFF_L1	Listing of Faecal Occult		SAC [2]
Labs					
19	All Subjects	LB6	Listing of Haematology Laboratory Data for Subjects with Abnormalities of Potential Clinical Importance		SAC [2]
20	All Subjects	LB6	Listing of Clinical Chemistry Laboratory Data for Subjects Abnormalities of Potential Clinical Importance		SAC [2]

CONFIDENTIAL

201881

ICH Listings					
No.	Population	IDSL / TST ID / Example Shell	Title	Programming Notes	Deliverable [Priority]
21	All Subjects	LB6	Listing of LFT's for Subjects Abnormalities of Potential Clinical Importance		SAC [2]
22	All Subjects	LB6	Listing of Clinical Chemistry Laboratory Data for Subjects Abnormalities of Potential Clinical Importance As a Change from Baseline	Rather than have the value and normal range column just include a change from baseline column	SAC [2]
23	All Subjects	LB6	Listing of Haematology Laboratory Data for Subjects with Abnormalities of Potential Clinical Importance As a Change from Baseline	Rather than have the value and normal range column just include a change from baseline column	SAC [2]
ECGs					
24	All Subjects	EG4	Listing of ECG Values for Subjects with Abnormalities of Potential Clinical Importance.		SAC [2]
Vital Signs					
25	All Subjects	VS5	Listing of Vital Signs for Subjects with Abnormalities of Potential Clinical Importance		SAC [2]
26	All Subjects	VS5	Listing of Vital Signs for Subjects		SAC [2]

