5.4. Screening/Baseline Failures

Screen failures are defined as subjects who consent to participate in the clinical trial but are not subsequently randomized. In order to ensure transparent reporting of screen failure subjects, meet the Consolidated Standards of Reporting Trials (CONSORT) publishing requirements, and respond to queries from Regulatory authorities, a minimal set of screen failure information is required including Demography, Screen Failure details, Eligibility Criteria, and any Serious Adverse Events.

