7.4.1.1. Time period and Frequency for collecting AE and SAE information

- AEs and SAEs will be collected from the start of Study Treatment until the follow-up contact (see Section [7.4.1.3](#)), at the timepoints specified in the Time and Events Table (Section [7.1](#)).
- Medical occurrences that begin prior to the start of study treatment but after obtaining informed consent may be recorded on the Medical History/Current Medical Conditions section of the CRF.
- Any SAEs assessed as related to study participation (e.g., protocol-mandated procedures, invasive tests, or change in existing therapy) or related to a GSK product will be recorded from the time a subject consents to participate in the study up to and including any follow-up contact.
- All SAEs will be recorded and reported to GSK within 24 hours, as indicated in [Appendix 5](#).
- Investigators are not obligated to actively seek AEs or SAEs in former study subjects. However, if the investigator learns of any SAE, including a death, at any time after a subject has been discharged from the study, and he/she considers the event reasonably related to the study treatment or study participation, the investigator must promptly notify GSK.

NOTE: The method of recording, evaluating and assessing causality of AEs and SAEs plus procedures for completing and transmitting SAE reports to GSK are provided in [Appendix 5](#)

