9.3. Data Analysis Considerations

9.3.1. Analysis Populations

All Subjects Population

The ‘All Subjects Population’ is defined as all randomized subjects who receive at least one dose of study medication.

Per Protocol Population

The ‘Per Protocol Population’ will consist of any Analysis Population subjects who are compliant with protocol-specific criteria. Subjects with specified protocol deviations will be excluded.

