5. ANALYSIS POPULATIONS

Population	Definition / Criteria	Analyses Evaluated
All Subjects	
 The 'All Subjects' Population is defined as all randomized subjects who receive at least one dose of study medication. 	
 • Study Population • Safety/tolerability •
Enrolled	All participants who sign informed consent and for whom a record exists on the study database. This population will be used for the tables/listings of reasons for withdrawal before randomization and listings of AEs and SAEs for non-randomized participants.	
 • Subject Disposition • Reasons for withdrawal before randomization. • Inclusion, exclusion, and randomization criteria deviations
Analysis Population	
 Subjects in the 'All Subjects' population having baseline and post-baseline assessments of the endpoint of interest for both periods 	
 • Efficacy • PD/Biomarker
Screening Population	
 The "Screening Population" is defined as all subjects who were screened as potential patients for the trial 	
 • Screen Failure
Per Protocol	
 Any 'Analysis Population' subjects who are compliant with protocol-specific criteria. Subjects with specified protocol deviations will be excluded. 	
 • Efficacy
PK Population	
 This population will include all subjects in the Safety Population for whom a pharmacokinetic blood sample was obtained and assayed. 	
 • Concentration data summaries,

Population	Definition / Criteria	Analyses Evaluated
		listings, and graphs (including concentration-time profiles as appropriate)
PK Parameter Population	
 This population will include all subjects in the PK Concentration Population for whom valid and evaluable pharmacokinetic parameters were derived. 	
 Listings, summary and analyses of PK parameters

NOTE :

- Please refer to Section [11.13 Appendix 11: List of Data Displays](#) which details the population to be used for each display being generated.

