11.13.4. Study Population Tables

Study Population Tables					
No.	Population	IDSL / TST ID / Example Shell	Title	Programming Notes	Deliverable [Priority]
Subject Disposition					
1.01	All Subjects	ES1	Summary of Subject Disposition		SAC [2]
1.02	Screening Population	ES6	Summary of Reasons for Screening Failure		SAC [2]
1.03	All Subjects	ES5	Summary of Reasons for Withdrawals		SAC [2]
1.04	All Subjects	DV1a	Summary of Important Protocol Deviations		SAC [2]
1.05	All Subjects	SA2	Summary of Deviations Leading to Exclusion from Per Protocol Population		SAC [2]
Demographics					
1.06	All Subjects	DM1	Summary of Demographic Characteristics	Make twice, pooled and by site	IA, SAC [2]
1.07	All Subjects	DM5	Summary of Race and Racial Combinations	Make twice, pooled and by site	SAC [2]
1.08	Enrolled	DM11	Summary of Age Ranges		SAC [2]
1.12	Enrolled	NS1	Summary of Number of Subjected by Country and Site ID		SAC[2]
1.09	All Subjects	SA1	Summary of Study Populations		SAC [2]
Medical Condition & Con Meds					
1.10	All Subjects	MH1	Summary of [Current/Past] Medical Conditions	Make twice, pooled and by site	SAC [2]

Study Population Tables					
No.	Population	IDSL / TST ID / Example Shell	Title	Programming Notes	Deliverable [Priority]
1.11	All Subjects	CM1	Summary of Most Frequently used Concomitant Medications by Generic Term	Footnote: Most Frequently means the overall concomitant medication used is $\geq 10\%$	SAC [2]

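### Listing 03 (screening-failure reasons) is empty by definition, and the SAE listing that SAP Section 5 promises for non-randomised participants is missing from Appendix 11

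*SAP*

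**What the plan says.** **Population definitions.** SAP Section 5 defines All Subjects as "all randomized subjects who receive at least one dose of study medication"; Protocol Section 9.3.1 gives the same definition. SAP Section 5 also sets up a Screening Population, "all subjects who were screened as potential patients for the trial", whose only stated use is screen failure. It sets up an Enrolled population, made up of everyone who has consented and has a record on the study database. Enrolled is to be used for subject disposition, reasons for withdrawal before randomisation, eligibility deviations and "listings of AEs and SAEs for non-randomized participants". A note to the same section points to Appendix 11 for the population of each display.

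**Display list.** In Appendix 11, Table 1.02, "Summary of Reasons for Screening Failure", is on the Screening Population. Listing 03, "Listing of Reasons for Screening Failure", is on All Subjects. Every AE and SAE table and listing is on All Subjects.

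**Protocol.** Section 5.4 states: "Screen failures are defined as subjects who consent to participate in the clinical trial but are not subsequently randomized". It includes any SAE in the minimum data set for these subjects. Section 7.4.1.1 says that SAEs related to study participation or to a GSK product "will be recorded from the time a subject consents to participate in the study up to and including any follow-up contact".

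**The concern.** A listing restricted to randomised and dosed subjects cannot show subjects who failed screening. The same restriction on the safety displays excludes anyone who consented but was never dosed, although the protocol collects certain SAEs from consent and SAP Section 5 undertakes to list them.

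The data at risk are not purely hypothetical. Protocol Sections 7.3.1 and 7.3.2 place a step exercise test on Day -1 of each period, so the first one precedes any dose. The risk table in Protocol Section 4.6.1 accepts that side effects of exercise can, rarely, be serious or life-threatening. If a subject with heart failure had such an event on Day -1 of Period I and was then not dosed, a study report built from Appendix 11 would not show it. In a trial this small (SAP Section 4.1 describes a prediction on 10 subjects, followed by one further enrolment), a single unlisted SAE would matter to a reader of the safety section.

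**Working it through.** No sample size, power or error rate is involved. The check is set logic on the population definitions, followed by a reading of every display in Appendix 11.

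**Step 1: Listing 03.**
- Population assigned: All Subjects = {randomised and dosed at least once} (SAP Section 5).
- Subjects it should show: screen failures = {consented and not randomised} (Protocol Section 5.4).
- Intersection: {randomised and dosed} ∩ {consented, not randomised} = ∅.

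The listing therefore has 0 rows whatever the data. Table 1.02 covers the same topic on the Screening Population, so the table and the listing contradict each other. In addition, the overview in SAP Section 7.1 (its Table 2) marks screening-failure reasons as a listing only, so the one output the overview promises is the empty one.

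**Step 2: AE and SAE displays in Appendix 11.**

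| Displays | Number | Population | Can include a never-dosed subject? |
|---|---|---|---|
| Tables 3.02 to 3.08 | 7 | All Subjects | No |
| Listings 12, 13, 14 | 3 | All Subjects | No |
| Total | 7 + 3 = 10 | All Subjects | 0 of 10 |

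**Step 3: where the other two populations are used.** Enrolled is used for 2 displays: Table 1.08 (age ranges) and Table 1.12 (subject counts by country and site). The Screening Population is used for 1 display, Table 1.02. None of these 3 carries AE or SAE data. The listing promised in SAP Section 5 therefore has no counterpart.

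**Step 4: who falls in the gap.** All Subjects selects people, not dates.
- Consented, never randomised: outside all 10 displays.
- Randomised, never dosed: outside all 10 displays.
- Dosed, with an SAE before the first dose: inside All Subjects. The programming notes exclude pre-treatment events only from Tables 3.02 to 3.04. Listings 12 and 13 and Tables 3.05 and 3.08 carry no such exclusion, and SAP Section 11.3.3 defines a pre-treatment AE state.

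The gap is confined to the first two groups.

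**Step 5: other items that SAP Section 5 gives to Enrolled.**
- Subject disposition: Table 1.01 is on All Subjects.
- Eligibility deviations: Listing 06 is on All Subjects.
- Reasons for withdrawal before randomisation: no display on Enrolled. Table 1.03 and Listing 02 concern withdrawals and are both on All Subjects.

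**The case against.** The strongest reply is that this is a clerical slip with little consequence. SAP Section 5 states the right intention for both screen failures and non-randomised participants, an empty listing would be noticed as soon as it was run, aggregate screen-failure reasons survive in Table 1.02, and no estimate or confidence interval moves. All of that is fair, and it limits the weight of the point. It does not remove it: SAP Section 5 itself names Appendix 11 as the place where each display's population is set. An empty listing is easy to notice; a listing that was never specified is not.

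Four stronger readings are tempting, and the documents do not support them.

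- *That any SAE in the screening period of up to 25 days is lost.* Step 4 shows that this is so only for subjects who are never dosed.
- *That such SAEs go unreported.* Protocol Section 7.4.1.1 sends SAEs to the sponsor within 24 hours, and Section 7.4.1.5 deals with regulatory reporting separately. What is missing is a display in the study report.
- *That SAP Section 5 requires Listing 02 and Table 1.01 to be on Enrolled.* For withdrawals, Section 5 names only those before randomisation, whereas Listing 02 covers study withdrawal. Moving it alone would separate it from Table 1.03. For disposition the SAP supports both populations: Section 5 lists it under Enrolled, but Section 7.1 includes it among analyses that default to All Subjects.
- *That many AEs are affected.* Under Protocol Section 7.4.1.1, AEs are collected from the start of study treatment and earlier occurrences may go to medical history. For never-dosed subjects the content is essentially the SAEs collected from consent.

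Listing number 27 is absent from Appendix 11, but nothing shows that it was the missing SAE listing.

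**Conclusion.** The point holds in two parts. First, Listing 03 is wrong as written: it has 0 rows by definition and conflicts with Table 1.02. Secondly, SAP Section 5 and Appendix 11 contradict each other: a listing for non-randomised participants is promised, and 0 of the 10 AE/SAE displays can deliver it. As a result, an SAE related to study procedures in a consented subject who is never dosed appears in no planned display.

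This rests on Appendix 11 being followed as written and on the All Subjects definition being applied literally. The documents give no count of screen failures or of randomised but undosed subjects, so the number of people affected cannot be derived and may be zero. No efficacy result, sample size or error rate changes. What is at stake is the completeness of screen-failure and safety reporting, so it should be corrected but does not threaten the trial's conclusions.

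**What to change.** 1. Assign Listing 03 to the Screening Population, matching Table 1.02.
2. Add one short listing of SAEs, with any AEs that were recorded, on the Enrolled population for subjects never randomised or never dosed.
3. Reconcile SAP Section 5 with SAP Section 7.1 and Appendix 11 on the population for Table 1.01 and Listing 06, and state the choice once.
4. Provide the pre-randomisation withdrawal reasons named in SAP Section 5 on Enrolled, and leave Listing 02 on the same population as Table 1.03.

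The cost is a few population labels, one short safety listing and a small display of pre-randomisation withdrawals. The protocol already collects the SAE and screen-failure data needed, and no modelling changes.

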11.13.11. Non-ICH Listings

Non-ICH Listings					
No.	Population	IDSL / TST ID / Example Shell	Title	Programming Notes	Deliverable [Priority]
Efficacy					
28	All Subjects	Non-Standard EFF_L1	Listing of Gas Diffusion Outcomes (DLco, DLno, Dm, Vc)		SAC [2]
29	All Subjects	Non-Standard EFF_L2	Listing of Gas Diffusion Outcomes Change from Baseline (DLco, DLno, Dm, Vc)		SAC [2]
30	All Subjects	Non-Standard EFF_L1	Listing of VE/VCO ₂	Rows for day -1 and day 7 only	SAC [2]
31	All Subjects	Non-Standard EFF_L2	Listing of VE/VCO ₂ Change from Baseline	Rows for day -1 and day 7 only	SAC [2]
32	All Subjects	PFT9	Listing of Pulmonary Function Test (FVC, FEV1, FEF-25-75, FEF50, FEF75)	Rows for day -1, day 4, and day 7 only	SAC [2]
33	All Subjects	Non-Standard EFF_L2	Listing of Pulmonary Function Test Change from Baseline (FVC, FEV1, FEF-25-75, FEF50, FEF75)	Rows for day -1, day 4, and day 7 only	SAC [2]
34	All Subjects	LB6	Listing of Troponin	(Include change from baseline)	SAC [2]
35	All Subjects	SF6	Listing of SF-36 Acute Score		SAC [2]
36	All Subjects	MOS_S7	Listing of Sleep Study Variables	Include Minimum Oxygen Saturation during sleep, total sleep time, central apnea index, obstructive apnea index, mixed apnea index, hypopnea index, apnea hypopnea index	SAC[2]

[figure not shown]
Non-ICH Listings					
No.	Population	IDSL / TST ID / Example Shell	Title	Programming Notes	Deliverable [Priority]
40	All Subjects	EFF_L2	Listing of Change in Minimum Oxygen Saturation during Polysomnography		SAC[2]
41	All Subjects	EFF_L1	Listing of AUC of HMG-CoA reductase inhibitors and their key metabolites		SAC[2]
37	All Subjects	SF6	Listing of Dyspnea Score	(Include change from baseline)	SAC[2]
PK					
38	PK	PKCL1P	Listing of Plasma GSK2798745 Pharmacokinetic Concentration-Time Data		SAC [2]
39	PK	PKPL1P	Listing of Derived Plasma GSK2798745 Pharmacokinetic Parameters	Include dose and dose number	SAC [2]

11.14. Appendix 12: Example Mock Shells for Data Displays

Example : EFF_F1
 Protocol : 201881
 Population : All Subjects

Page 1 of X

Figure 1.1
 Spaghetti Plot of DLco Data
 DLco by Patient

[figure not shown]
NOTE: Plot adjusted accordingly to study data

Example : EFF_F2
 Protocol : 201881
 Population : All Subjects

Page 1 of X

Figure 1.02
 Mean (95% CI) Plot of DLco

Mean DLCO per Visit, by Treatment

[figure not shown]
NOTE: Plot adjusted accordingly to study data.

Example : EFF_F3
Protocol : 201881
Population : All Subjects

Page 1 of X

Figure 1.03
Mean (95% CI) Plot of DLco

Mean Chronic DLco by
Treatment Group

[figure not shown]
NOTE: Plot adjusted accordingly to study data.

Example : EFF_F4
 Protocol : 201881
 Population : All Subjects

Page 1 of X

Figure 1.04
 Plot of DLco by Individual and Treatment

DLco Over Time by Treatment Group

[figure not shown]
NOTE: Plot adjusted accordingly to study data.

Example : EFF_F5
Protocol : 201881
Population : All Subjects

Page 1 of X

Figure 1.05
Change from Baseline DLco by Individual and Treatment

Change from Baseline Chronic DLco by
Treatment Group

[figure not shown]
NOTE: Plot adjusted accordingly to study data.

Example : EFF_F6
Protocol : 201881
Population : All Subjects

Page 1 of X

Figure 1.06
Mean Plot of DLco Change from Baseline

Mean Change from Baseline DLco by Treatment Group

[figure not shown]
NOTE: Plot adjusted accordingly to study data.

Example : EFF_F7
Protocol : 201881
Population : All Subjects

Page 1 of X

Figure 1.07
Mean Plot of DLco Pre/Post Exercise

Mean DLco Pre/Post Exercise by
Treatment Group

[figure not shown]
NOTE: Plot adjusted accordingly to study data.

Example : EFF_F8
Protocol : 201881
Population : All Subjects

Page 1 of X

Figure 1.08
Mean Plot of DLco Change from Exercise

Mean Change from Exercise DLCO by Treatment Group

[figure not shown]

NOTE: Plot adjusted accordingly to study data.

Example : EFF_F9
Protocol : 201881
Population : All Subjects

Page 1 of X

Figure 1.09
Mean Plot of Percent Change DLco from Exercise

[figure not shown]
NOTE: Plot adjusted accordingly to study data.

Example : EFF_F10
Protocol : 201881
Population : All Subjects

Page 1 of X

Figure 1.10
Mean Plot of Percent Change DLco from Saline

Mean Percent Change from Saline DLCO by
Treatment Group

[figure not shown]

NOTE: Plot adjusted accordingly to study data.

Example : EFF_F11
 Protocol : 201881
 Population : All Subjects

Page 1 of X

Figure 1.11
 Plot of VE/VCO₂

[figure not shown]
NOTE: Plot adjusted accordingly to study data.

Example : EFF_F12
Protocol : 201881
Population : All Subjects

Page 1 of X

Figure 1.12
Mean (95% CI) Plot of VE/VCO₂

Average Ve/VCO₂ Ratio by Treatment

[figure not shown]

NOTE: Plot adjusted accordingly to study data.

Example : EFF_F13
Protocol : 201881
Population : All Subjects

Page 1 of X

Figure 1.13
Plot of VE/VCO₂ Change from Day -1

[figure not shown]
NOTE: Plot adjusted accordingly to study data.

Example : EFF_F14
Protocol : 201881
Population : All Subjects

Page 1 of X

Figure 1.14
Plot of Mean VE/VCO₂ Change from Day -1

Average Change from Day -1
Ve/VCO₂ Ratio by Treatment

[figure not shown]

NOTE: Plot adjusted accordingly to study data.

Example : EFF_F15
 Protocol : 201881
 Population : All Subjects

Page 1 of X

Figure 1.15
 Plot of VE/VCO₂ Change from Rest

[figure not shown]
NOTE: Plot adjusted accordingly to study data.

Example : EFF_F16
Protocol : 201881
Population : All Subjects

Page 1 of X

Figure 1.16
Plot of Mean VE/VCO₂ Change from Rest

Mean VE/VCO₂ Ratio Change from Rest

[figure not shown]

NOTE: Plot adjusted accordingly to study data.

Example : EFF_F17
Protocol : 201881
Population : All Subjects

Page 1 of X

Figure 1.17
Spaghetti Plot of FVC

[figure not shown]

NOTE: Plot adjusted accordingly to study data.

Example : EFF_F18
Protocol : 201881
Population : All Subjects

Page 1 of X

Figure 1.18
Mean (95% CI) Plot of FVC

[figure not shown]

NOTE: Plot adjusted accordingly to study data.

Example : EFF_F19
Protocol : 201881
Population : All Subjects

Page 1 of X

Figure 1.19
Mean (95% CI) Plot of FVC Change from Baseline

[figure not shown]

NOTE: Plot adjusted accordingly to study data.

Example : EFF_F20
Protocol : 201881
Population : All Subjects

Page 1 of X

Figure 1.20
Individual Plot of 24-Hour Respiratory Monitoring

[figure not shown]

NOTE: Plot adjusted accordingly to study data.

Example : EFF_F21
Protocol : 201881
Population : All Subjects

Page 1 of X

Figure 1.21
Mean (95% CI) Plot of 24 Hour Respiratory Rate Monitoring

[figure not shown]

NOTE: Plot adjusted accordingly to study data.

Example : EFF_F22
Protocol : 201881
Population : All Subjects

Page 1 of X

Figure 1.22
DLco Spaghetti Plot by Site

[figure not shown]
NOTE: Plot adjusted accordingly to study data.

Example : EFF_F23
 Protocol : 201881
 Population : All Subjects

Page 1 of X

Figure 1.23
 Forest Plot of End Points

Absolute Change of DL End-Points
 n=10

[figure not shown]

NOTE: Plot adjusted accordingly to study data, text values are the mean change from baseline.

Example : EFF_F24
 Protocol : 201881
 Population : All Subjects

Page 1 of X

Figure 1.24
 DLco Saline Challenge Graph

NOTE: Plot adjusted accordingly to study data. The text is the difference between before and after and the percent change

Example : EFF_T1
 Protocol : 201881
 Population : Analysis

Page 1 of X

Table 1.01
 Summary Statistics of DLco

Visit	Treatment	N	n	Mean	SD	Mean Percent Predicted	Percent Predicted SD
	Screen	X	X	XX.X	XX.XX	XX.X	XX.XX
	Baseline	A	X	X	XX.X	XX.XX	
Baseline after exercise	A	X	X	XX.X	XX.XX		
	Day 4	A	X	X	XX.X	XX.XX	
	Day 5	A	X	X	XX.X	XX.XX	
Day 5 after saline infusion	A	X	X	XX.X	XX.XX		
	Day 7	A	X	X	XX.X	XX.XX	
	Day 7 after exercise	A	X	X	XX.X	XX.XX	
	Baseline	B	X	X	XX.X	XX.XX	
Baseline after exercise	B	X	X	XX.X	XX.XX		
	Day 4	B	X	X	XX.X	XX.XX	
	Day 5	B	X	X	XX.X	XX.XX	
Day 5 after saline infusion	B	X	X	XX.X	XX.XX		
	Day 7	B	X	X	XX.X	XX.XX	
	Day 7 after exercise	B	X	X	XX.X	XX.XX	
	Follow-up	NA	X	X	XX.X	XX.XX	

Example : EFF_T2
 Protocol : 201881
 Population : Analysis

Page 1 of X

Table 1.02
 Summary Statistics of DLco Change from Baseline

Visit	Treatment	N	n	Mean	SD
Baseline after exercise	A	X	X	XX.X	XX.XX
	Day 4	X	X	XX.X	XX.XX
	Day 5	X	X	XX.X	XX.XX
Day 5 after saline infusion	A	X	X	XX.X	XX.XX
	Day 7	X	X	XX.X	XX.XX
	Day 7 after exercise	X	X	XX.X	XX.XX
Baseline after exercise	B	X	X	XX.X	XX.XX
	Day 4	X	X	XX.X	XX.XX
	Day 5	X	X	XX.X	XX.XX
Day 5 after saline infusion	B	X	X	XX.X	XX.XX
	Day 7	X	X	XX.X	XX.XX
	Day 7 after exercise	X	X	XX.X	XX.XX

Example : EFF_T3
 Protocol : 201881
 Population : Analysis

Page 1 of X

Table 1.03
 Summary Statistics of DLno

Visit	Treatment	N	n	Mean	SD
	Screen	X	X	XX.X	XX.XX
	Baseline	A	X	XX.X	XX.XX
Baseline after exercise	A	X	X	XX.X	XX.XX
	Day 4	A	X	XX.X	XX.XX
	Day 5	A	X	XX.X	XX.XX
Day 5 after saline infusion	A	X	X	XX.X	XX.XX
	Day 7	A	X	XX.X	XX.XX
Day 7 after exercise	A	X	X	XX.X	XX.XX
	Baseline	B	X	XX.X	XX.XX
Baseline after exercise	B	X	X	XX.X	XX.XX
	Day 4	B	X	XX.X	XX.XX
	Day 5	B	X	XX.X	XX.XX
Day 5 after saline infusion	B	X	X	XX.X	XX.XX
	Day 7	B	X	XX.X	XX.XX
Day 7 after exercise	B	X	X	XX.X	XX.XX
	Follow-up	NA	X	XX.X	XX.XX

Example : EFF_T4
Protocol : 201881
Population : Analysis

Page 1 of X

Table 1.04
Summary Statistics of FVC

Visit	Treatment	N	n	Mean	SD
Baseline	A	X	X	XX.X	XX.XX
Day 4	A	X	X	XX.X	XX.XX
Day 7	A	X	X	XX.X	XX.XX
Baseline	B	X	X	XX.X	XX.XX
Day 4	B	X	X	XX.X	XX.XX
Day 7	B	X	X	XX.X	XX.XX
Follow-up	NA	X	X	XX.X	XX.XX

Example : EFF_T5
Protocol : 201881
Population : Analysis

Page 1 of X

Table 1.05
Summary Statistics of FVC Change from Baseline

Visit	Treatment	N	n	Mean	SD
Day 4	A	X	X	XX.X	XX.XX
Day 7	A	X	X	XX.X	XX.XX
Day 4	B	X	X	XX.X	XX.XX
Day 7	B	X	X	XX.X	XX.XX

Example : EFF_T6
Protocol : 201881
Population : Analysis

Page 1 of X

Table 1.06
Summary of Statistical Analysis Results of DLco

Treatment	Placebo	Adjusted Mean	
		Difference Estimate	95% CI
XX.XX	XX.XX	XX.XX	(XX.XX, XX.XX)

NOTE: Table adjusted accordingly to the study data, with model details added as footnotes.

CONFIDENTIAL

201881

Example : EFF_T7
 Protocol : 201881
 Population : Analysis

Page 1 of X

Table 1.07
 Summary Statistics of Ve/VCO₂ Ratio

Period	Sequence	Treatment	N	Visit	Mean At Rest	SD At Rest	Mean Post 1 Min	SD Post 1 Min	Mean Post 2 Min	SD Post 2 Min	Mean Post 3 Min	SD Post 3 Min	Mean Recovery	SD Recovery
1	AB	A	X	Baseline	XX.X	XX.XX	XX.X	XX.XX	XX.X	XX.XX	XX.X	XX.XX	XX.X	XX.XX
				Day 7	XX.X	XX.XX	XX.X	XX.XX	XX.X	XX.XX	XX.X	XX.XX	XX.X	XX.XX
2	AB	B	X	Baseline	XX.X	XX.XX	XX.X	XX.XX	XX.X	XX.XX	XX.X	XX.XX	XX.X	XX.XX
				Day 7	XX.X	XX.XX	XX.X	XX.XX	XX.X	XX.XX	XX.X	XX.XX	XX.X	XX.XX
Follow-up	AB	NA	X	Follow-up	XX.X	XX.XX	XX.X	XX.XX	XX.X	XX.XX	XX.X	XX.XX	XX.X	XX.XX
1	BA	B	X	Baseline	XX.X	XX.XX	XX.X	XX.XX	XX.X	XX.XX	XX.X	XX.XX	XX.X	XX.XX
				Day 7	XX.X	XX.XX	XX.X	XX.XX	XX.X	XX.XX	XX.X	XX.XX	XX.X	XX.XX
2	BA	A	X	Baseline	XX.X	XX.XX	XX.X	XX.XX	XX.X	XX.XX	XX.X	XX.XX	XX.X	XX.XX
				Day 7	XX.X	XX.XX	XX.X	XX.XX	XX.X	XX.XX	XX.X	XX.XX	XX.X	XX.XX
Follow-up	BA	NA	X	Follow-up	XX.X	XX.XX	XX.X	XX.XX	XX.X	XX.XX	XX.X	XX.XX	XX.X	XX.XX

CONFIDENTIAL

201881

Example : EFF_T8
 Protocol : 201881
 Population : Analysis

Page 1 of X

Table 1.08
 Summary Statistics of Ve/VCO₂ Ratio Change from Baseline

Period	Sequence	Treatment	N	Visit	Mean At Rest	SD At Rest	Mean Post 1 Min	SD Post 1 Min	Mean Post 2 Min	SD Post 2 Min	Mean Post 3 Min	SD Post 3 Min	Mean Recovery	SD Recovery
1	AB	A	X	Day 7	XX.X	XX.XX	XX.X	XX.XX	XX.X	XX.XX	XX.X	XX.XX	XX.X	XX.XX
2	AB	B	X	Day 7	XX.X	XX.XX	XX.X	XX.XX	XX.X	XX.XX	XX.X	XX.XX	XX.X	XX.XX
Follow-up	AB	NA	X	Follow-up	XX.X	XX.XX	XX.X	XX.XX	XX.X	XX.XX	XX.X	XX.XX	XX.X	XX.XX
1	BA	B	X	Day 7	XX.X	XX.XX	XX.X	XX.XX	XX.X	XX.XX	XX.X	XX.XX	XX.X	XX.XX
2	BA	A	X	Day 7	XX.X	XX.XX	XX.X	XX.XX	XX.X	XX.XX	XX.X	XX.XX	XX.X	XX.XX
Follow-up	BA	NA	X	Follow-up	XX.X	XX.XX	XX.X	XX.XX	XX.X	XX.XX	XX.X	XX.XX	XX.X	XX.XX

Example : EFF_T9
 Protocol : 201881
 Population : Analysis

Page 1 of X

Table 1.09
 Summary Statistics of Dyspnea

Visit	Treatment	N	n	Mean	SD	Median	Range	Percent of Patients with at Least 1-Point Improvement ¹	Frequency of Item Scores				
									1	2	3	4	5
Baseline Pre-Exercise	A	X	X	XX.X	XX.XX	XX.X	X - X		X	X	X	X	X
Baseline Post-Exercise	A	X	X	XX.X	XX.XX	XX.X	X - X	XX.XX	X	X	X	X	X
Day 5 Sitting	A	X	X	XX.X	XX.XX	XX.X	X - X	XX.XX	X	X	X	X	X
Day 5 Supine	A	X	X	XX.X	XX.XX	XX.X	X - X	XX.XX	X	X	X	X	X
Day 7 Pre-Exercise	A	X	X	XX.X	XX.XX	XX.X	X - X	XX.XX	X	X	X	X	X
Day 7 Post-Exercise	A	X	X	XX.X	XX.XX	XX.X	X - X	XX.XX	X	X	X	X	X
Baseline Pre-Exercise	B	X	X	XX.X	XX.XX	XX.X	X - X		X	X	X	X	X
Baseline Post-Exercise	B	X	X	XX.X	XX.XX	XX.X	X - X	XX.XX	X	X	X	X	X
Day 5 Sitting	B	X	X	XX.X	XX.XX	XX.X	X - X	XX.XX	X	X	X	X	X
Day 5 Supine	B	X	X	XX.X	XX.XX	XX.X	X - X	XX.XX	X	X	X	X	X
Day 7 Pre-Exercise	B	X	X	XX.X	XX.XX	XX.X	X - X	XX.XX	X	X	X	X	X
Day 7 Post-Exercise	B	X	X	XX.X	XX.XX	XX.X	X - X	XX.XX	X	X	X	X	X
Follow-up	NA	X	X	XX.X	XX.XX	XX.X	X - X		X	X	X	X	X

Example : EFF_T11
 Protocol : 201881
 Population : Analysis

Page 1 of X

Table 1.11
 Summary Statistics of Respiratory Rate

Day -1				Day 4				Day 7			
Treatment		Placebo		Treatment		Placebo		Treatment		Placebo	
Mean	SD	Number of Hours Included	Mean	SD	Number of Hours Included	Mean	SD	Number of Hours Included	Mean	SD	Number of Hours Included

Lying
 Standing
 Leaning

Example : EFF_T12
Protocol : 201881
Population : Analysis

Page 1 of X

Table 1.12
Summary Statistics of DLco Change from Intervention

Visit	Treatment	N	n	Mean	SD
Baseline change from exercise	A	X	X	XX.X	XX.XX
Day 5 change from saline infusion	A	X	X	XX.X	XX.XX
Day 7 change from exercise	A	X	X	XX.X	XX.XX
Baseline change from exercise	B	X	X	XX.X	XX.XX
Day 5 change from saline infusion	B	X	X	XX.X	XX.XX
Day 7 change from exercise	B	X	X	XX.X	XX.XX

Example : EFF_L1
Protocol : 201881
Population : All Subjects

Page 1 of X

Listing 1
Listing of Gas Diffusion

Sequence	Treatment	Subject	Visit	DLco	DLno	D _M	VE/VCO ₂
AB		1	Screening				
			Period 1 Baseline				
	A		Period 1 Day -1 Post Exercise				
	A		Period 1 Day 4				
	A		Period 1 Day 5				
	B		Period 1 Day 5 Post-Saline				
			Period 2 Baseline				
	B		Period 2 Day -1 Post Exercise				
	B		Period 2 Day 4				
	B		Period 2 Day 5				
	B		Period 2 Day 5 Post-Saline				
			Follow-Up				

Example : EFF_L2
Protocol :
Population : Safety

Page 1 of X

Listing 2
Listing of Gas Diffusion Change from Baseline

Sequence	Treatment	Subject	Visit	Change in DLco	Change in DLno	Change in D_M	Change in VE/VCO ₂
AB	A		Period 1 Day -1 Post Exercise				
			Period 1 Day 4				
			Period 1 Day 5				
			Period 1 Day 5 Post-Saline				
	B		Period 2 Day -1 Post Exercise				
			Period 2 Day 4				
			Period 2 Day 5				
			Period 2 Day 5 Post-Saline
